Description American Society of Anesthesiologists Physical Status Classification System.

Available IPD/Information:

U.S. National Library of Medicine | U.S. National Institutes of Health | U.S. Department of Health & Human Services

Official title: China Medical University Hospital

NCT number: NCT04595253

Title: The Effectiveness of Acupressure for Managing Postoperative Pain and Anxiety in Patients With Thoracoscopic Surgery

Statistical Analysis Plan

SPSS statistical software was used for data analysis, independent t test and chi-square test were used for descriptive analysis. A mixed model with repeated analysis was used to examine the effect of acupressure on pain, anxiety, and comfort. Regression analysis was to explore the influences of pain, anxiety, and comfort for study patients with thoracoscopic Surgery.

Primary Completion Date

The patient experienced moderate pain and anxiety after thoracoscopic surgery. There was no significant difference in demographic characteristics between the two groups before they received surgery. The experimental group, compared with the control group, pain intensity ($p<0.01$) and anxiety score ($p<0.05$) were statistically significant lower on day 1 and day 2 after intervention. The STAI-Y1 score ($F=2.514$, $p=.086$) and comfort level ($F=2.953$, $p=.057$) were no significant differences after intervention between two groups. The longer intervention, the significantly decreased pain intensity ($p<0.05$) for surgical procedures with lighter pain perception.

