Detailed Description: Thoracoscopic surgery is the surgical used to removal of a section or a segment of a lung lobe. One US national survey reported that 80% of patients undergoing pulmonary surgery experienced acute pain. 75-86% of these patients pointed out that experienced moderate, severe, or extreme pain, especially, on the 1st day after thoracoscopic surgery. However, inappropriate pain management after surgery is associated with limited the healing process, increased workload of heart, prolonged pulmonary rehabilitation, and increased medical costs, and can be a prediction of developing chronic pain. Acupressure is a nonpharmacological treatment for the management of postoperative pain. Recent studies have found that the application of acupressure is effective in decreasing operative pain intensity, morphine related side effects, and opioid consumptions after surgery. However, there was no further research about the role of acupressure applied to thoracoscopic surgery.

Conditions

Conditions: Lung Diseases

Keywords: acupressure
thoracoscopic surgery
acute pain
anxiety
comfort

Study Design

Study Type: Interventional

Primary Purpose: Supportive Care

Study Phase: N/A

Interventional Study Model: Parallel Assignment

Number of Arms: 2

Masking: Single (Participant)

Allocation: Randomized

Enrollment: 200 [Anticipated]

Arms and Interventions

| Arms | Assigned Interventions |
|---|--|
| Experimental: acupressure After recruitment, participants will be randomized to receive acupressure or control group. In the | acupressure The acupressure involves the " Vaccaria Semen" within skin-colored adhesive tape that placed on |

| Arms | Assigned Interventions |
|--|---|
| acupressure group, participants will receive acupressure treatment. | the "Neiguan" and "Shenmen" acupoints as an intervention measure. Continue to massage the acupoints with fingertips for 10 minutes, 3 times per day (8 and 12 in the morning, and 4 in the afternoon). The adhesive tape will be retained in situ for 2 days. |
| No Intervention: routine care After recruitment, participants will be randomized to receive acupressure or control group. In the control group, participants will receive routine care, including routine pain control. | |

Outcome Measures

Primary Outcome Measure:

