1. Pain: Changes from baseline pain scale at post-operative day 2, after intervention. as assessed by Visual Analogue Scale-Pain (VAS-P). The VAS#P scale is comprised of a horizontal line 100mm long with the indication "no pain" to the left and "worst possible pain" to the right. possible scores varied between 0–100. A higher scores mean a worse outcome.

[Time Frame: Measure at before operation day, 7 post meridiem (PM), before operation; post-operative day1, 8 ante meridiem (AM), before intervention; post-operative day 1, 5 PM, after intervention; and post-operative day 2, 5 PM, after intervention]

Secondary Outcome Measure:

2. Anxiety as assessed by Visual Analogue Scale-Anxiety(VAS-A). The VAS#A scale is comprised of a horizontal line 100mm long with the indication "no anxiety" to the left and "worst possible anxiety" to the right. possible scores varied between 0–100. A higher scores mean a worse outcome.

[Time Frame: Measure at before operation day, 7 post meridiem (PM), before operation; post-operative day1, 9 ante meridiem (AM), before intervention; post-operative day 1, 5 PM, after intervention; and post-operative day 2, 5 PM, after intervention.]

3. Anxiety as assessed by State-Trait Anxiety Inventory (STAI) Y form (STAI-Y1). It is 20 questions, which were rated from 1–4. Possible scores varied between 20–80. A STAI-Y1 score>40 as evidence of a state of anxiety.

[Time Frame: Time Frame: Measure at before operation day, 7 post meridiem (PM), before operation; post-operative day1, 8 ante meridiem (AM), before intervention; and post-operative day 2, post meridiem (PM), after intervention.]

Other Pre-specified Outcome Measures:

4. Analgesia Consumption
Injection time of morphine and ketorolac would be recorded.

[Time Frame: during the whole admission, an average of 4 day.]

5. Comfort as assessed by Shortened General Comfort Questionnaire

[Time Frame: Measure at before operation day,7 post meridiem (PM), before operation; post-operative day 1, 8 ante meridiem (AM), before intervention; and post-operative day 2, 5pm, after intervention]

6. Heart rate variability as assessed by Nexus-10, wireless Biofeedback/Neurofeedback system

[Time Frame: Measure at before operation day, 7 post meridiem (PM), before operation; post-operative day1, 8 ante meridiem (PM), before intervention; post-operative day 1, 5 post meridiem (PM), after intervention; and post-operative day 2, 5 PM, after intervention.]

7. Early ambulation

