The first ambulation time: act to walk with or without any kind of assistant after operation.

Eligibility

Minimum Age: 20 Years

Maximum Age:

Sex: All

Gender Based:

Accepts Healthy Volunteers: Yes

Criteria: Inclusion Criteria:

- pulmonary lung disease and will be scheduled to undergo a thoracoscopic wedge resection, segmentectomy, or lobectomy.
- American Society of Anesthesiologist physical status of Classes I-II,
- both forearms without missing limbs or arteriovenous fistula
- ability to communicate in Taiwanese or Chinese, and
- agreement to participate in this study.

Exclusion Criteria:

- diagnosed as malignant neoplasm with lung meta,
- Had a stroke or peripheral vascular disease
- Platelet count less than $20 \times 10^3/\text{mm}^3$
- Using the patient controlled analgesia, and
- any known mental illness or memory dysfunction.

Contacts/Locations

Central Contact Person: [name]

[contact] [name]

Email: [contact]

Central Contact Backup: [name]

Study Officials: [name]

Study Principal Investigator

China Medical University, China

Locations: **Taiwan**

China Medical University

[Recruiting]

Taichung, Taiwan, 40447

Contact: [name], PHD [name]

[contact]

Contact: [name], PHD [name] [contact]

Principal Investigator: [name]

Sub-Investigator: [name]

IPDSharing

Plan to Share IPD: No

References

Citations: **[Study Results]** Abouarab AA, Rahouma M, Kamel M, Ghaly G, Mohamed A. Single Versus Multi-Incisional Video-Assisted Thoracic Surgery: A Systematic Review and Meta-analysis. *J Laparoendosc Adv Surg Tech A*. 2018 Feb;28(2):174-185. doi: 10.1089/lap.2017.0446. Epub 2017 Nov 6. Review. PubMed 29106318

Amico, T. A. D. (2007). Thoracoscopic Lobectomy. *Journal of Medical Sciences*, 27(3), 95-100. [https://doi.org/10.6136/JMS.2007.27\(3\).095](https://doi.org/10.6136/JMS.2007.27(3).095)

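### The SAP's mixed model names no POD2 pain contrast, baseline or covariates; a POD2 difference adjusted for scores already collected would fill the gap and is usually more precise

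*Combined protocol and SAP*

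**What the plan says.** Under Outcome Measures, Primary Outcome 1 (Pain), the registered endpoint is "Changes from baseline pain scale at post-operative day 2, after intervention". Its time frame has four assessments. Two precede treatment: "Measure at before operation day, 7 post meridiem (PM), before operation; post-operative day1, 8 ante meridiem (AM), before intervention". Two follow it: "post-operative day 1, 5 PM, after intervention; and post-operative day 2, 5 PM, after intervention". The word baseline is attached to neither of the first two.

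The Statistical Analysis Plan gives one inferential sentence for pain: "A mixed model with repeated analysis was used to examine the effect of acupressure on pain, anxiety, and comfort". It states no model terms, covariance structure, visit contrast, baseline or covariates. The t test and chi-square test are assigned to descriptive analysis.

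The results text under Primary Completion Date says "pain intensity ($p<0.01$) and anxiety score ($p<0.05$) were statistically significant lower on day 1 and day 2 after intervention". It gives no difference in mm and no confidence interval.

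Study Design anticipates 200 participants in two arms. Arms and Interventions places randomization after recruitment, with no day or hour, and the control arm receives routine care without a sham.

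**The concern.** The registered endpoint cannot be computed until a baseline is chosen, and the SAP does not choose one. Pre-op pain and pain on the first morning after surgery are different measurements, so in a single data set the two change scores can give different estimates. The mixed model does not close the gap, because the sentence in the SAP could cover many models and does not say which of their terms is the primary result.

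Precision is also at stake. A change score subtracts the whole of a noisy earlier measurement, and a plain POD2 comparison ignores it. Regression on the earlier scores uses as much of them as predicts POD2. These scores are already in hand, yet the plan gives them no role.

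**Working it through.** The plan has no power calculation or SD, so there is no design figure to reproduce. What follows is illustrative.

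**Inputs**
- From the documents: 200 participants, two arms, two pre-intervention and two post-intervention VAS-P scores.
- Assumed: equal allocation (100 per arm), complete data, equal SD at every visit. The correlation r of pre-op with each post-op score is 0.3 (range 0.1 to 0.5). The correlation s between post-op scores is 0.5 (range 0.3 to 0.7).

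**Step 1. Variance per patient, in units of the POD2 variance**
- Plain POD2: 1.
- Change from pre-op: 2 − 2r = 2 − 0.6 = 1.4.
- Change from POD1 8 AM: 2 − 2s = 2 − 1.0 = 1.0.
- POD2 adjusted for both scores: 1 − R², where R² = (r² + s² − 2r²s)/(1 − r²) = (0.09 + 0.25 − 0.09)/0.91 = 0.275. The variance is 0.725.
- POD2 adjusted for pre-op only: 1 − r² = 0.91.

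**Step 2. Patients needed relative to the two-score adjustment**

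| Analysis | Central | Range over the assumed correlations |
|---|---|---|
| Change from POD1 8 AM | 1.0/0.725 = 1.38 | 1.18 to 1.88 |
| Plain POD2 | 1.0/0.725 = 1.38 | 1.10 to 2.08 |
| Change from pre-op | 1.4/0.725 = 1.93 | 1.34 to 3.54 |

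If the pre-op SD is half the post-op SD, the last ratio falls to 1.31 (1.00 to 2.26).

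**Step 3. 95% CI half-width at 100 per arm, 1.96 × √(2 × variance/100), in SD units**
- Adjusted for both: 0.24.
- Adjusted for pre-op only: 1.96 × √(0.0182) = 0.26.
- Plain POD2 and change from POD1 8 AM: 0.28.
- Change from pre-op: 0.33.

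**Step 4. Zero correlation.** Two useless covariates inflate the variance by (N − 3)/(N − 5) = 197/195 = 1.010 at N=200, a loss of about 1% against plain POD2.

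**Step 5. Does the baseline choice drop out?** Subtracting a covariate from the outcome changes only that covariate's coefficient (by −1). In one simulated data set, the two-score model gave −0.3535 (SE 0.1199) whether the outcome was POD2, change from pre-op or change from POD1 8 AM. Without adjustment, the same data gave −0.380, −0.577 and −0.258.

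**Step 6. If allocation itself shifted the POD1 8 AM score.** The slope on that score is (s − r²)/(1 − r²) = 0.41/0.91 = 0.45. A 0.2 SD shift in that score alone moves the two-score estimate by 0.2 × 0.45 = 0.09 SD. The largest slope in the assumed range is 0.69/0.99 = 0.70 (r = 0.1, s = 0.7), which gives 0.14 SD. Change from POD1 8 AM would move by the full 0.2 SD.

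**The case against.** The registration section does fix the primary timepoint, so the gap is in the SAP's model and in the word baseline. The missing estimate and CI come from a short results paragraph, and on their own would be a reporting complaint. Both points stand.

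The precision ratios rest on correlations that the documents do not give, and the comparators are change scores and a plain comparison, whereas the SAP names a mixed model. A mixed model that constrained the pre-intervention means to be equal between arms would be about as precise as the adjusted contrast. This also stands, although the SAP does not say that it used such a model.

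The most serious objection concerns the POD1 8 AM score. Allocation may have been known by then, there is no sham, and the first daily massage is also listed at 8 in the morning. If allocation shifted that score, the two baselines would no longer lead to the same target, and adjusting for it would bias the POD2 difference. The two-score model therefore needs a condition. The objection weighs still more against change from POD1 8 AM.

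A reader might infer that the choice of baseline could have reversed the reported significance for pain. The documents do not support this, since they give no effect, SD or correlation. At the central correlations and 100 per arm, the two change scores disagreed at the 5% level in about 32% of simulated trials at a true effect of 0.4 SD, but in 5% at 0.6 and 0.4% at 0.8. The reported wording suggests visit-specific comparisons, but does not show whether they were adjusted. The F statistics printed for STAI-Y1 and comfort concern other outcomes and do not reveal the form of the pain test.

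**Conclusion.** The concern holds as a gap in the analysis plan that should be fixed. The primary contrast, the baseline and the role of the two earlier scores are undefined.

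An adjusted POD2 difference is usually more precise than either change score or a plain POD2 comparison, by about 1.4 to 1.9 times in patients at the central assumptions. That size depends on the assumed correlations, equal SDs, equal allocation and complete data.

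A reader might conclude that adjusting for both scores resolves everything without cost. The documents do not support that, for three reasons:
- The timing of allocation and its disclosure relative to POD1 8 AM is not stated.
- Missing covariate scores need their own rule.
- With correlations near zero there is a small efficiency loss.

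If only the pre-op score can safely be used, the gain is smaller: the variance is 0.91 against 1.0 for plain POD2 and 1.4 for change from pre-op. Change from POD1 8 AM could then be nominally more precise (when s exceeds about 0.55, where 2 − 2s falls below 0.91), but it would carry the whole of any allocation-driven shift.

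**What to change.** 1. Report one primary result: the acupressure-minus-control difference in VAS-P at POD2 5 PM, in mm with a 95% CI. Treat POD1 5 PM as secondary.
2. Take it from a mixed model of POD1 5 PM and POD2 5 PM (REML, unstructured covariance, Satterthwaite df) with group, visit, group-by-visit, the pre-intervention score or scores, and the interaction of each score with visit. The interactions are needed for the model to reproduce the POD2 ANCOVA in complete data.
3. State when allocation was made and disclosed, and whether the POD1 8 AM score was taken before the first massage. If patients could not know their arm before that score, adjust for both scores, which makes the choice of baseline irrelevant. If they could, adjust for the pre-op score only in the primary model and show the two-score model as a sensitivity analysis.
4. Fill a missing pre-intervention score by a rule that ignores arm, such as the overall mean, so that no randomized patient with a post-intervention score is dropped. The likelihood handles missing outcomes only.
5. Label the re-analysis post hoc, because results are already reported.

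The cost is SAP wording, a record of allocation timing and a re-run of one model on existing data (plus the sensitivity model if step 3 calls for it). The statistical downside is an efficiency loss of about 1% at N=200 if the correlations are zero.

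### The conclusion that longer intervention lowered pain cannot come from this design: every treated patient is assigned the same 2-day course, and the procedure subgroup is not defined

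*Combined protocol and SAP*

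**What the plan says.** Arms and Interventions describes a single acupressure regimen: "Continue to massage the acupoints with fingertips for 10 minutes, 3 times per day", and "The adhesive tape will be retained in situ for 2 days". The record gives "Number of Arms: 2". The other arm receives no intervention: "In the control group, participants will receive routine care, including routine pain control". No arm has a shorter or longer course.

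For the primary outcome (VAS-P), the assessments after treatment starts are at "post-operative day 1, 5 PM, after intervention; and post-operative day 2, 5 PM, after intervention". The time frame is not restricted to one arm.

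The inclusion criteria admit "thoracoscopic wedge resection, segmentectomy, or lobectomy". None of the three is labelled as more or less painful.

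The Statistical Analysis Plan names t and chi-square tests for descriptive comparison, a repeated-measures mixed model for the effect of acupressure on pain, anxiety and comfort, and a regression: "Regression analysis was to explore the influences of pain, anxiety, and comfort". It names no duration term, procedure term, subgroup or interaction, and it lists no covariates for the regression.

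The text under the Primary Completion Date heading then ends with: "The longer intervention, the significantly decreased pain intensity ($p<0.05$) for surgical procedures with lighter pain perception". It gives no test, contrast, subgroup size, mean, SD or degrees of freedom for this statement.

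**The concern.** The closing sentence makes two claims at once: that more intervention gave less pain, and that this held for certain operations. The first needs patients whose assigned length of treatment differed, and there are none. The second needs a defined set of operations and a test that the arm effect differs across them. Neither is in the documents.

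At stake is a secondary conclusion reported with a p-value. As worded, it could be taken as evidence on how long to treat and in which operations. The primary outcome, change in VAS-P to post-operative day 2, is not affected.

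**Working it through.** **1. The reported figure.** The p<0.05 cannot be reproduced, because the documents give no n, mean, SD, df or test for it.

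**2. Planned exposure at each assessment.** Inputs: 10 minutes per session, 3 sessions per day (Arms and Interventions); a pre-intervention measurement at 8 AM on day 1 and post-intervention measurements at 5 PM on days 1 and 2 (primary outcome).
- By day 1, 5 PM: 3 × 10 = 30 minutes.
- By day 2, 5 PM: 6 × 10 = 60 minutes.

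These values are the same for every treated patient, and they are zero for every control.

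**3. Can duration be separated from day?** Take a model with intercept, arm, day 1, day 2, arm × day 1 and arm × day 2 (6 columns), and add a column for cumulative minutes. For every row,

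minutes = 30 × (arm × day 1) + 60 × (arm × day 2).

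The seventh column is an exact combination of two columns already present. The matrix has 7 columns and rank 6, so a duration effect has no estimate separate from the arm-by-day terms. This does not depend on sample size or software.

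**4. What a within-arm test would do.** The documents do not say that this test was used; the calculation shows the consequence if it was. Assumptions, none from the documents:
- no acupressure effect;
- a natural decline of 0.3 or 0.5 SD from day 1 to day 2;
- within-patient correlation ρ = 0.5;
- subgroup size 33 or 17 treated patients. Equal arms and three equal procedure groups give 200/2/3 ≈ 33 at the anticipated enrolment of 200, and 100/2/3 ≈ 17 at half of it.

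For a paired t test, d_z = decline/√(2(1 − ρ)) = decline/√1 = decline, and the non-centrality is d_z√n. Two-sided α is 0.05.

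| Decline | n treated in subgroup | Non-centrality | Chance of p<0.05 |
|---|---|---|---|
| 0.3 SD | 33 | 0.3 × √33 = 1.72 | 39% |
| 0.3 SD | 17 | 0.3 × √17 = 1.24 | 21% |
| 0.5 SD | 33 | 0.5 × √33 = 2.87 | 80% |
| 0.5 SD | 17 | 0.5 × √17 = 2.06 | 49% |

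**5. What an arm-by-day test would do instead.** In a simulation with no acupressure effect (5,000 runs, 33 per arm in the subgroup, assumed SD 20 mm, correlation 0.5, natural recovery 5, 10 or 15 mm), the within-arm test gave p<0.05 in about 28%, 78% and 99% of runs. The comparison of changes between arms stayed at 4.8% to 5.7%.

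**6. Do the documents hint at which test was used?** The same results text reports F=2.514, p=.086 for STAI-Y1 and F=2.953, p=.057 for comfort, without df. With 2 numerator df these pairs fit about 92–112 and 86–105 denominator df. With 1 numerator df neither fits. With 3, they fit only at about 20–21 denominator df. Both outcomes have three time points, so an arm-by-time test would have 2 numerator df. This is an inference, and it concerns other outcomes.

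**The case against.** The strongest reply is that a controlled analysis may lie behind the sentence. Both arms have the same assessment schedule, a repeated-measures mixed model is named, and the F and p pairs in step 6 are what an arm-by-time test would give. This stands, and it limits the point. A reader might infer that there is no controlled comparison behind the p-value, or that natural recovery has been credited to acupressure. The documents support neither: they do not state the test, and they give no course of pain over time in the control arm. Still, an arm-by-time result would show only that the difference between arms changes from day 1 to day 2. It could not attribute the change to longer treatment.

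A reader might also call the subgroup unplanned. The regression is too vaguely described to settle this; procedure may or may not have been a covariate. What can be said is that the subgroup is neither specified nor defined in the documents supplied.

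Nor does the text report a non-significant result in another procedure group. The familiar error of contrasting a significant subgroup with a non-significant one may be suspected, but it is not shown.

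Whole-arm sizes would make the illustration look worse: for a 0.3 SD decline, 84% with 100 treated patients and 55% with 50. They do not apply, because the sentence concerns only some procedures.

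Finally, the minutes of massage actually delivered could vary between patients. The documents describe no record of this, and a comparison on it would not be randomised.

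**Conclusion.** The point holds in this form. The sentence makes a statement about length of intervention, and the design as assigned cannot inform one, because length and post-operative day are exactly collinear. This follows from the regimen and needs no assumption beyond treatment as planned. The procedure-specific part has no definition and no reported interaction test.

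Whether recovery explains the p-value is conditional. If the test was within-arm, recovery alone would produce significance in about 21% to 80% of trials across the assumed declines (0.3 to 0.5 SD) and subgroup sizes (17 to 33 treated patients), at correlation 0.5. If it was arm-by-day, recovery common to both arms is removed, and the finding becomes a difference that changes by day. The documents do not allow a choice between the two. The sentence should be changed in either case, although it is a secondary conclusion.

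**What to change.** 1. Remove the statement about length of intervention.
2. From the mixed model already named, report the arm-by-day contrast on VAS-P: (day 2, 5 PM minus day 1, 5 PM) in acupressure minus the same difference in control, with estimate and 95% CI. Describe it by post-operative day.
3. If a procedure-specific statement is kept, fit arm × day × procedure with the three enrolled procedures as levels. Report that interaction with n per arm and procedure and the df, and label it exploratory. Separate arm-by-day and arm-by-procedure tests would not be enough, because the claim joins day and procedure.

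The cost is one re-run of the model and the rewording of one sentence. The downside is that the claim may weaken or disappear.
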